#### **4.1.2 United States**

This study will be conducted in compliance with institutional review board (IRB) and ICH GCP Guidelines - including Title 21 Part 56 of the United States of America (USA) Code of Federal Regulations (CFR) relating to IRBs and GCP as described in the United States Food and Drug Administration (FDA) CFR (21 CFR § 50, 56, 312) - in accordance with applicable ICH regulations regarding clinical safety data management (E2A, E2B(R3)), and with ICH regulations regarding scientific integrity (E4, E8, E9, and E10). In addition, this study will adhere to all local regulatory requirements, and requirements for data protection.

Before initiating a trial/study, the Investigator/institution must have written and dated approval/favorable opinion from the IRB for the study protocol/amendment(s), written ICF, any consent form updates, subject recruitment procedures (e.g., advertisements), and any written information to be provided to subjects and a statement from the IRB that these materials comply with GCP requirements. The IRB approval must identify the protocol version as well as the documents reviewed.

### **4.2 Ethical Conduct of the Study**

This study will be conducted in accordance with the Note for Guidance on GCP (ICH Harmonised Tripartite Guideline E6 (R1)/Integrated Addendum E6 (R2); FDA CFR (21 CFR § 50, 56, 312)), requirements for the conduct of clinical studies as provided in the EU Directive 2001/20/EC, the general guidelines indicated in the Declaration of Helsinki (Seoul 2008) ([Appendix 1, Section 17.1](#)) and all applicable regulatory requirements.

#### 4.3 Subject Information and Consent

The Investigator will explain the benefits and risks of participation in the study to each subject, the subject's legally acceptable representative, or impartial witness, and obtain written informed consent. Written informed consent must be obtained prior to the subject entering the study and before initiation of any study-related procedure (including administration of investigational product [IP]).

The Sponsor will provide a sample ICF, based on the elements of informed consent in [Appendix 2 \(Section 17.2\)](#). The final, version-dated form must be agreed to by the Sponsor and the IRB/IEC and will contain all elements in the sample form, in language readily understood by the subject. Each subject's original consent form, personally signed and dated by the subject or by the subject's legally acceptable representative, and by the person who conducted the informed consent discussion, will be retained by the Investigator. The Investigator will supply all enrolled subjects with a copy of their signed informed consent.

The consent form may need to be revised during the study should important new information become available that may be relevant to the consent of the subject. In this instance, approval should always be given by the IRB/IEC and existing subjects informed of the changes and reconsented. This is documented in the same way as previously described.

## 6. INTRODUCTION

### 6.1 Disease Review

Type 1 diabetes usually results from cellular autoimmune destruction of the beta cells in the pancreas, severely reducing or eliminating production of endogenous insulin. Without insulin, glucose cannot enter cells and blood glucose concentration increases. Hepatic gluconeogenesis may ensue, further elevating the blood glucose concentration. Without treatment, potentially life-threatening ketoacidosis may develop [1].

Diabetes is a chronic, progressive disease that, if inadequately treated, can lead to significant morbidity, including macrovascular and microvascular complications, and significantly increased mortality. In conjunction with ongoing patient lifestyle education regarding self-management of the disease, subcutaneous insulin is the mainstay of treatment for patients with type 1 diabetes [1].

The Diabetes Control and Complications Trial (DCCT) [2] demonstrated that intensive therapy with subcutaneous insulin leads to improved glycemic control and better outcomes. Since the publication of the DCCT, several insulin analogs have been developed that are associated with a lower risk of hypoglycemia in patients with type 1 diabetes and lowering of glycosylated hemoglobin (HbA1c) equivalent to human insulin [2]. Ratner et al [3] showed that compared with human insulin, treatment with insulin glargine was associated with lower fasting glucose concentrations and a lower incidence of hypoglycemia. Hasslacher et al [4] showed that subjects with type 1 diabetes and early stage chronic kidney disease who were treated with insulin analogs such as insulin glargine had better kidney function and higher hemoglobin concentrations, compared with those who received human insulin.

### 6.2 Compound Review – Insulin Glargine

Insulin glargine is a biosynthetic insulin analog with a longer duration of action than human insulin. The substitution of glycine for asparagine at A21 and the addition of 2 arginines at the C-terminus of the B chain result in stabilization of the molecule, leading to delayed and prolonged absorption after subcutaneous injection [3, 5].

#### 6.2.1 Nonclinical Studies

An extensive characterization and comparison of structural and biofunctional properties of Gan & Lee Insulin Glargine Injection and Lantus® has been conducted [6]. The structural characterization (including primary, secondary, tertiary and quaternary structures; size, hydrophobicity, charge heterogeneities, and cell-based biofunctionality including the binding to the receptors of insulin and insulin-like growth factor-1), and the activation of the insulin-signaling cascade and the stimulation of glucose uptake were demonstrated to be similar between Gan & Lee Insulin Glargine Injection and Lantus®. For in vitro and in vivo pharmacologic and toxicologic studies and clinical studies, reference is made to NDA 021081 [5].

### 6.2.2 Clinical Studies

In 2016, Study GL-GLA-001, a phase I, exploratory, randomized, double-blind, 2-way crossover pilot study, demonstrated bioequivalence of Gan & Lee Insulin Glargine Injection and United States (US)-sourced Lantus®. Although this exploratory study suggested biosimilarity, it was not powered to provide robust statistical conclusions. Gan & Lee Insulin Glargine Injection was well tolerated, and treatment-emergent adverse events were comparable to those with Lantus®. There were no significant signals that would indicate a difference in the safety profile between the treatments. A pivotal phase I study will be performed concurrently to assess the pharmacokinetic (PK) and pharmacodynamic effects of Gan & Lee Insulin Glargine Injection compared with US- and European-sourced Lantus®.

### 6.3 Clinical Study Rationale

The purpose of this study is to compare Gan & Lee Insulin Glargine Injection 100 U/mL with that of the reference medicinal product, Lantus®, Sanofi-Aventis' brand of insulin glargine injection 100 U/mL, and evaluate equivalence in terms of immunogenicity, safety, and efficacy, in subjects with type 1 diabetes mellitus.

Insulin analogs are more costly than conventional insulins, and limited access to affordable insulin may keep some patients from accessing important treatment options, leading to unnecessary complications [1, 7].

Biosimilar products may result in significant price reductions compared to the cost of the reference products, even if the reductions are not of the magnitude seen with many generics [8].

Biosimilar drugs are not identical to the reference product. Because even small differences in the primary structure can result in clinically significant functional differences, there are concerns about potential risks to patients [8]. Insulin glargine has been shown to exhibit proliferative and anti-apoptotic effects in vitro in colorectal cancer cells; however, clinical studies have produced conflicting results regarding an association between insulin glargine and cancer risk [9]. And although a number of observational studies in 2009 found an association between insulin glargine and an increased risk for breast cancer in patients with type 2 diabetes, a recent study of more than 12,000 subjects with type 2 diabetes who were newly started on insulin glargine showed no increase in the risk of breast cancer after a median 5-year follow-up period among those who were insulin-naïve. A nonsignificant increase in risk was found among subjects who had switched to insulin glargine from other insulins [10].

Because biosimilar insulins have immunogenic potential, the European Medicines Agency (EMA) and the FDA require an evaluation of safety and immunogenicity between biosimilars and their reference products, and the EMA has indicated these studies should be of sufficient duration (at least 6 to 12 months) to detect these differences. This study is designed in accordance with the guidance documents provided by the EMA [11] and the FDA [12].

The immunogenicity assessment will use the one-assay [13] and tiered approach [14]. Samples collected at all time points (including pre-dose) from both treatment groups will first be tested using the validated electrochemiluminescence method [15]. The rate and degree of immunogenicity, and data interpretation will also include consideration of other clinical attributes such as (but not limited to) symptoms of hypersensitivity or injection site reactions and the PK profile.

## 7. STUDY OBJECTIVES

### 7.1 Primary Study Objective:

- To evaluate equivalence of Gan & Lee Insulin Glargine Injection and Lantus® in terms of immunogenicity

### 7.2 Secondary Study Objectives:

#### 7.2.1 Immunogenicity

- To evaluate the percentage of subjects with negative anti-insulin antibodies (AIAs) at baseline who develop confirmed positive AIA up to visit Week 26, the percentage of subjects with at least a 4-fold increase in titers compared to baseline value, mean change from baseline in AIA titers between treatment groups, the percentage of subjects with confirmed positive AIA who develop any anti-insulin neutralizing antibodies up to visit Week 26, and the percentage of subjects in each treatment group with confirmed positive AIA up to visit Week 26 of Gan & Lee Insulin Glargine Injection in comparison with that of Lantus®

#### 7.2.2 Safety

- To evaluate the safety of Gan & Lee Insulin Glargine Injection in comparison with that of Lantus®

#### 7.2.3 Efficacy

- To evaluate the efficacy of Gan & Lee Insulin Glargine Injection in comparison with that of Lantus®

### 7.3 Exploratory Study Objectives:

- To investigate the retrospective hypoglycemic rate and the time in hypoglycemia and hyperglycemia using continuous glucose monitoring (CGM) data
- To examine the relationship between the plasma concentrations of insulin glargine, M1, and M2, and immunogenic response

## 8. INVESTIGATIONAL PLAN

### 8.1 Overall Study Design and Plan

The purpose of this equivalence study is to compare the immunogenicity, safety, and efficacy of Gan & Lee Insulin Glargine Injection with that of the reference medicinal product, Lantus®, in adults with type 1 diabetes mellitus.

At the screening visit, subjects will sign the informed consent form (ICF), they will be screened for eligibility, and the following information will be collected: adverse events, medical history (including diabetes mellitus and thyroid disease history), prior and concomitant medications, vital signs, height, body weight, and body mass index (BMI). The following procedures will be performed: 12-lead electrocardiogram (ECG), physical examination, and blood collection for fasting blood glucose (FBG) test, HbA1c, A1A, and routine hematology and chemistry testing (complete blood count, metabolic chemistry panel with serum lipids, thyroid-stimulating hormone [TSH], and free thyroxine [T4]). A urinalysis, and for women of childbearing potential, a urine pregnancy test will be performed. At this visit, the subject will be issued a glucometer, test strips, and other supplies, and the Investigator or designee will provide instruction and conduct training on how to use the glucometer for prospective glucose monitoring to document hypoglycemic episodes in a prospective manner. Subjects will be allowed to keep the glucometer after the study, per local ethical and legal guidelines and regulations. Subjects will also receive a Hypoglycemic Events Record in which they will record information about any hypoglycemic events that occur during their participation in the study.

During the 2 weeks between screening and randomization, subjects will have their insulin dosing optimized according to [Table 3](#) in [Section 8.5.8](#).

Also, at the screening visit, the subject will have a FreeStyle Libre Pro Flash Glucose Monitoring sensor applied to the back of the upper arm according to the manufacturer's instructions.

The FreeStyle Libre Pro Flash Monitoring System is approved by the EMA for people 18 years of age or older with diabetes. The FreeStyle Libre Pro Flash Glucose Monitoring System sensor, which requires 12 to 24 hours to calibrate itself after application, will be worn for 8 days and will record the interstitial fluid glucose every 15 minutes. Data from the 2nd through the 8th days of wear will be used for each analysis. The sensor will be blinded to the subject and no subject action will be needed. The subject will also be issued a Mealtime & Insulin Dose Record in which they will record the time of their meals, and insulin use. After 8 days, the subject may remove the sensor, place in the biohazard bag provided and bring it with them to the randomization visit. If the end of the 8-day continuous glucose monitoring (CGM) period coincides with the date of the randomization visit, the sensor can be removed at the visit. Subjects will bring both their Hypoglycemic Events Record and their Mealtime & Insulin Dose Record to the randomization visit.

Subjects who meet the study eligibility criteria will be centrally randomized 1:1 in an open-label fashion to receive either Gan & Lee Insulin Glargine or Lantus® for 26 weeks.

Randomization will be stratified by country. Subjects will continue using their bolus insulin

but will substitute IP for their basal insulin. The Sponsor will ensure that all insulins will be provided to all subjects regardless of medical insurance or reimbursement issues.

At the randomization visit (Visit 2), subjects will receive supply of insulin kits with IP and the Investigator or designee will train subjects on all study procedures and proper dose administration.

Subjects in both treatment groups will be assessed every 2 weeks after Visit 2 (randomization visit) through Week 22 (telephone call); and then at Week 26; they will attend a total of 9 clinic visits (the screening visit, the randomization visit, and at Weeks 2, 4, 8, 12, 16, 20, and 26), 2 brief visits during which a CGM sensor will be applied (8-10 days before the visits at Weeks 12 and 26), and they will be contacted by telephone at Weeks 6, 10, 14, 18, and 22. The Week 26 visit (Visit 9) will be the end-of-treatment visit.

At all planned visits and phone contacts (except for visits to apply a CGM sensor) the Investigator or designee will review glucose results (especially looking for hypoglycemia), adverse events, changes in concomitant medications, and changes in IP or bolus insulin use, and the following procedures will be performed: vital signs, body weight, urinalysis, urine pregnancy testing for women of childbearing potential, and an FBG test.

[figure not shown]
Additional procedures at study visits are as follows: at Weeks 8, 16 and 26, blood for HbA1c will be collected; during the visits at Weeks 12 and 26, subjects will wear their CGM sensors to the site for the site staff to safely remove it, and they will bring their Mealtime & Insulin Dose Record for the site staff to review, and blood will be collected for routine hematology and chemistry testing, TSH and free T4 and TSH; at Weeks 12 and 26, blood will be collected for AIA; and at Week 26, a 12-lead ECG and physical examination will be performed.

A subset of additionally consented subjects will have blood drawn at Day 1 and Weeks 2, 4, 8, 12, 16, 20, and 26 for optional PK (insulin glargine, M1, and M2 concentrations).

If a subject discontinues the study prematurely, site personnel will make a reasonable effort to perform all study activities scheduled for Visit 9 (end of treatment [EOT] visit).

Additionally, it is very important for site personnel to encourage subjects to visit the site at Week 26 ( $\pm$  4 weeks) (and Week 12  $\pm$  1 week if applicable) for a blood sample to be obtained for AIA and HbA1c measurements.

Figure 1 and Table 1 show the study design and study-related procedures, respectively.

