6.3.2 Safety

- The incidence and severity of all treatment-emergent adverse events (TEAE) and the following subgroups:
 - Hypoglycemia, which will be fully documented in the Hypoglycemic Events Record, using data from subject report (symptomatic), FBG from central lab, study issued glucometer and CGM
 - SAEs, including fatal events
 - Adverse events leading to termination of the study treatment and/or early withdrawal from the study
 - IP-related AEs
 - Injection site reactions
- The incidence of clinically significant laboratory abnormalities
- The incidence of clinically significant abnormalities in electrocardiogram (ECG) and vital signs

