7.3 Safety

1) American Diabetes Association (ADA) Severe Hypoglycemic AE

A hypoglycemic AE will be classified as "ADA-severe" if the answer to the question "Was third party intervention required for this episode of hypoglycemia?" is Yes on the Hypoglycemia CRF page as mentioned in the ADA hypoglycemia position statement (3).

ADA Severe Hypoglycemic AE should not be confused with hypoglycemia AEs that are graded severe (Grade 3) per National Cancer Institute Common Terminology Criteria for Adverse Events (NCI CTCAE) grade (see Section 11.8.2.1).

2) Adverse Event Leading to Discontinuation of IP

An AE will be classified as an AE leading to discontinuation of IP if the answer to the question "Did the adverse event cause the subject to be discontinued from the study?" is Yes on the AE CRF page.

3) Hypoglycemic AE

An AE will be classified as a hypoglycemic AE if the answer to the question "Is this a hypoglycemic event?" is Yes on the AE CRF page.

4) Injection Site Reactions

Injection site reactions will be identified using the Medical Dictionary for Regulatory Activities (MedDRA) High Level Term = "Injection site reaction".

5) IP-related adverse events

An AE will be classified as related to IP if the relationship to study treatment is Possibly Related, Probably Related, or Definitely Related. Additionally, if the relationship is missing, then the AE will be deemed IP-related.

6) Persistent/Non-persistent Hypoglycemic AE

Hypoglycemic event with Time in hypoglycemia (see definition in Section 7.4) greater or equal to an hour (per CGM) would be classified as persistent. A hypoglycemic event with Time in hypoglycemia below an hour (per CGM) would be classified as non-persistent.

7) Symptomatic Hypoglycemic AE

A Hypoglycemic AE will be classified as symptomatic if the answer to the question "Was subject aware of symptoms?" is Yes on the Hypoglycemia CRF page.

8) Treatment-emergent adverse events

Treatment-emergent adverse event (TEAE) is an event that started or worsened in severity on or after the day of the first dose of IP but not more than 30 days after the subject's last dose of IP.

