Additionally, the hypoglycemic event rate will be compared between treatment groups using a negative binomial regression model (Table 6, Analysis 11). The response variable in the model will be the number of hypoglycemia events. The model will include factors for treatment group and site. Site has been included as a factor as different handling of documentation of hypoglycemia event are identified. The logarithm (to base e) of the follow-up time will be used as an offset variable in the model to adjust for subjects having different exposure times. The estimated treatment effect and the corresponding 95% CI, as well as the 2-sided p-value will be presented.

A sample SAS code fragment is provided below for reference:

```
proc genmod data = <data>;
  class trt site;
  model count = trt site / dist = negbin offset = time_log;
  lsmeans trt / ilink diff exp cl;
run;
```

All TEAEs will be listed for subjects in the SS. A listing of all TEAEs leading to discontinuation of IP will be provided.

All non-treatment-emergent AEs recorded on the CRF will be listed separately for all screened subjects.

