11.8.2 Hypoglycemic Treatment Emergent Adverse Events

Hypoglycemic AEs which are only documented on the AE page and for whom the Hypoglycemia page is blank or missing will not be considered in the analyses which are described below.

On the Hypoglycemia page further details are documented if the answer to the question "Is this a hypoglycemic event?" on the Adverse Event page is 'Yes'. Hypoglycemic TEAEs will be reported using data recorded on both the Adverse Event page and the Hypoglycemia page as follows:

- Severe Hypoglycemic event (Table 6, Analysis 6)
- Symptomatic Hypoglycemic event (Table 6, Analysis 9)

nutrition disorders				"Was third party intervention required for this episode of hypoglycemia?" is Yes
---------------------	--	--	--	--

Additionally, summary of ADA graded hypoglycemic event and TEAE by ERIPD subgroup will be produced for per protocol analysis set 2 and 3 (Table 6, Analysis 12).

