Metabolism and nutrition disorders	Hypocalcemia	Corrected serum calcium of $<\text{LLN}$ - 8.0 mg/dL; $<\text{LLN}$ - 2.0 mmol/L; Ionized calcium $<\text{LLN}$ - 1.0 mmol/L	Corrected serum calcium of <8.0 - 7.0 mg/dL; <2.0 - 1.75 mmol/L; Ionized calcium <1.0 - 0.9 mmol/L; symptomatic	Corrected serum calcium of <7.0 - 6.0 mg/dL; <1.75 - 1.5 mmol/L; Ionized calcium <0.9 - 0.8 mmol/L; hospitalization indicated	Corrected serum calcium of <6.0 mg/dL; <1.5 mmol/L; Ionized calcium <0.8 mmol/L; life-threatening consequences
Investigations	Creatinine increased	>1 - $1.5 \times$ baseline; $>\text{ULN}$ - $1.5 \times \text{ULN}$	>1.5 - $3.0 \times$ baseline; $>\text{ULN}$ - $3.0 \times \text{ULN}$	$>3.0 \times$ baseline; >3.0 - $6.0 \times \text{ULN}$	$>6.0 \times \text{ULN}$
Metabolism and nutrition disorders	Hyperglycemia	Fasting glucose value $>\text{ULN}$ - 160 mg/dL; Fasting glucose value $>\text{ULN}$ - 8.9 mmol/L	Fasting glucose value >160 - 250 mg/dL; Fasting glucose value >8.9 - 13.9 mmol/L	Fasting glucose value >250 - 500 mg/dL; >13.9 - 27.8 mmol/L; hospitalization indicated	>500 mg/dL; >27.8 mmol/L; life-threatening consequences
Metabolism and nutrition disorders	Hypoglycemia	Fasting glucose value $<\text{LLN}$ - 55 mg/dL; $<\text{LLN}$ - 3.0 mmol/L	<55 - 40 mg/dL; <3.0 - 2.2 mmol/L	<40 - 30 mg/dL; <2.2 - 1.7 mmol/L	<30 mg/dL; <1.7 mmol/L; life-threatening consequences; seizures
Metabolism and nutrition disorders	Hyperkalemia	Blood potassium value $>\text{ULN}$ - 5.5 mmol/L	>5.5 - 6.0 mmol/L	>6.0 - 7.0 mmol/L; hospitalization indicated	>7.0 mmol/L; life-threatening consequences
Metabolism and nutrition disorders	Hypokalemia	Blood potassium value $<\text{LLN}$ - 3.0 mmol/L	$<\text{LLN}$ - 3.0 mmol/L; symptomatic; intervention indicated	<3.0 - 2.5 mmol/L; hospitalization indicated	<2.5 mmol/L; life-threatening consequences
Metabolism and nutrition disorders	Hyponatremia	Plasma sodium $<\text{LLN}$ - 130 mmol/L	-	<130 - 120 mmol/L	<120 mmol/L; life-threatening consequences
Metabolism and nutrition disorders	Hypernatremia	Plasma sodium $>\text{ULN}$ - 150 mmol/L	>150 - 155 mmol/L	>155 - 160 mmol/L; hospitalization indicated	>160 mmol/L; life-threatening consequences

Gan & Lee Pharmaceuticals USA

PRA HEALTH SCIENCES

Sponsor: Gan & Lee Pharmaceuticals USA Corporation
Protocol no: GL-GLAT1-3001

Statistical Analysis Plan
Version Date: 27-May-2021

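### The between-arm hypoglycemia rate model counts any event ticked as hypoglycemic, with no glucose or severity cut-off, so mild events can dilute its ratio and open-label reporting can shift it

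*Protocol*

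**What the plan says.** **Recording.** Protocol 8.1 gives subjects a Hypoglycemic Events Record "in which they will record information about any hypoglycemic events that occur during their participation in the study". Protocol 11.3 makes hypoglycemia an adverse event of special interest. Neither section gives a glucose value or a symptom rule. SAP 6.3.2 says that hypoglycemia is documented "using data from subject report (symptomatic), FBG from central lab, study issued glucometer and CGM", again with no cut-off for any source.

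**Classification.** SAP 7.3, item 3: "An AE will be classified as a hypoglycemic AE if the answer to the question" on the adverse event form, asking whether this is a hypoglycemic event, is Yes.

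**Model.** In the SAP text after Table 6, "the hypoglycemic event rate will be compared between treatment groups using a negative binomial regression model" (Analysis 11). "The response variable in the model will be the number of hypoglycemia events". The factors are treatment and site, with log follow-up time as offset, and the output is a 95% CI and a two-sided p-value. The SAP explains that site was added because hypoglycemia was found to be documented differently between sites.

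**A documentation filter.** SAP 11.8.2 says that events recorded only on the adverse event page, "for whom the Hypoglycemia page is blank or missing will not be considered in the analyses which are described below". Table 6 assigns Analysis 11 to Section 11.8.2, but the model is described before that heading, so it is unclear whether the filter applies to it. Either way it is a filter on paperwork, not on glucose.

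**Stricter definitions elsewhere.** SAP Appendix 2 sets CTCAE Grade 2 hypoglycemia at "<55 - 40 mg/dL; <3.0 - 2.2 mmol/L". SAP 7.3, item 1, defines ADA-severe events by third-party intervention. SAP 7.4 and 11.7.3.1 use 3.0 mmol/L for CGM.

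**Blinding.** Protocol 8.5.5 states that the trial is open-label. Protocol 8.1 says that the CGM sensor is blinded to the subject.

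**The concern.** The model's rate ratio answers whether the two arms report hypoglycemia equally often. For a basal insulin biosimilar the safety question is whether they have the same rate of clinically important hypoglycemia. The two answers can differ by two routes.

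- **Dilution.** If most counted events are minor and do not differ by treatment, a real difference in the important ones is averaged away. No bias is needed. Because a ratio near 1 will be read as reassuring, this error runs in the unsafe direction.
- **Differential reporting.** Subjects and staff know the treatment. If events are reported more readily in one arm, the ratio moves even when the products are identical. The site factor removes habits that both arms share at a site, but not habits that differ by arm.

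**Working it through.** The documents give no hypoglycemia rate, effect size, margin or power, so there is no planned figure to reproduce. The inputs from the documents are 275 subjects per arm (Protocol 12.2), 26 weeks of treatment and the form of the model. Event shares, rates and dispersion below are assumptions, shown over a range.

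**1. Dilution.** Let s be the share of counted events in the reference arm that are mild and unaffected by treatment, and R the true rate ratio for the rest. The expected ratio of counts is s + (1 − s) × R. For false differences, take identical products and 20% more reporting of mild events in one arm; the ratio is then 1.2 × s + (1 − s).

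| s | Apparent ratio when R = 1.5 | Spurious ratio when products are identical |
|---|---|---|
| 0.5 | 0.5 + 0.5 × 1.5 = 1.25 | 0.6 + 0.5 = 1.10 |
| 0.8 | 0.8 + 0.2 × 1.5 = 1.10 | 0.96 + 0.2 = 1.16 |
| 0.9 | 0.9 + 0.1 × 1.5 = 1.05 | 1.08 + 0.1 = 1.18 |

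**2. What the model would detect.** The Wald approximation for a negative binomial comparison is SE(log RR) = √[(1/μ₁ + 1/μ₂ + 2k)/275], tested two-sided at 0.05. The assumptions are 10 to 40 reported events per subject over 26 weeks and dispersion k from 0.5 to 2. For example, with μ₁ = 10, ratio 1.20 and k = 1, SE = √[(0.100 + 0.083 + 2)/275] = 0.089, and log 1.20 / 0.089 = 2.05, so power is 53%.

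If important events truly double (R = 2):

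| Important share of counted events | Ratio of all counts | Power, all-events model |
|---|---|---|
| 5% | 1.05 | 7–12% |
| 10% | 1.10 | 12–34% |
| 20% | 1.20 | 32–84% |

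A model of the important events alone, with k from 1 to 3, has power of 97% or more. The least favourable case has μ₁ = 0.5 and k = 3: SE = √[(2 + 1 + 6)/275] = 0.181, and 0.693/0.181 − 1.96 = 1.87, giving 97%.

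With no true difference, reporting all events 10%, 20% or 30% more often in one arm gives a significant result in 12–34%, 32–84% or 57–99% of trials.

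**3. What the site factor does.** A simulation used 550 subjects, 50 sites, a mean of 10 events, k = 1, site reporting varying with a log-scale SD of 0.7, and 200 runs per setting. Habits that differed by site but not by arm left the adjusted ratio at 1.002. Reporting 20% more in one arm passed straight through, at 1.199, and was significant in 48.5% of runs. Dispersion was treated as known. With no arm difference, rejection was 6–9% (Monte Carlo SE about 2 points), so the percentages are approximate.

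**4. CGM coverage.** Wear days 2 to 8 give 7 analysed days at each of two post-randomization periods: 14 of 26 × 7 = 182 days, or 7.7%.

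**The case against.** **The stricter measures already exist.** This is the strongest reply, and in part it stands. The retrospective CGM event rate has a 3.0 mmol/L threshold and a sensor the subject cannot read, and it is meant to find events that subjects miss. It does not depend on reporting. Table 6 also plans CTCAE-graded, severe, serious and ADA summaries. A reader might infer that the plan has no threshold-based view of hypoglycemia; it has several. But Protocol 12.10 plans the CGM rate as a summary of an exploratory endpoint covering about 8% of follow-up, and in the readable text the other classes are tabulated, not modelled.

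**The text is incomplete.** In the copy available for review, SAP 11.7.3.1 breaks off and 11.8.2.1 and 11.8.2.2 are largely missing. A reader might infer that Analysis 11 is certainly the sole between-arm comparison; that cannot be established. The forest plot of adverse event terms also compares arms, though by risk difference on the same reported events.

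**The model is supplementary.** The protocol summarizes safety descriptively, and the SAP introduces Analysis 11 as an addition, with no margin and no place in a testing hierarchy. That stands: nothing in the readable text makes a hypoglycemia conclusion rest on this model alone.

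**The dilution figures assume that mild events are unaffected.** This too is fair. If mild events also rose, say by a ratio of 1.25, the 80%-mild case would give 0.8 × 1.25 + 0.2 × 1.5 = 1.30, not 1.10.

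**A threshold does not cure open-label bias.** Protocol 8.6.2 leaves self-testing to the investigator's instructions, so unblinded subjects and staff can still influence when glucose is measured and which events are entered. A cut-off reduces dilution and discretionary reporting, not differences in testing.

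**Conclusion.** The point holds as a cheap improvement to a supplementary safety analysis. In the readable SAP, the between-arm hypoglycemia rate model counts every adverse event ticked as hypoglycemic, with no glucose or severity cut-off. Its ratio can therefore be diluted by mild events, or shifted by arm-dependent reporting that the site factor leaves in place.

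The sizes are illustrative. A true 1.5 appearing as 1.05 to 1.25 rests on assumed mild shares of 50% to 90% and on mild events not responding to treatment. A spurious 1.10 to 1.18 rests on the same shares and on an assumed 20% excess in reporting. The documents contain no evidence that such an excess occurred: the SAP reports differences in documentation between sites, not between arms.

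**What to change.** In SAP 11.8.1/11.8.2, add a second run of the Analysis 11 model with the response restricted to hypoglycemic treatment-emergent adverse events that have a recorded lowest glucose below 3.0 mmol/L or third-party intervention. Present it beside the all-reported-events model. State also whether the Hypoglycemia-page filter in 11.8.2 applies to both.

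The data appear to be available: Table 6, Analysis 5, already grades events on lowest measured glucose, and SAP 7.3 places the third-party question on the Hypoglycemia page. The readable text does not say on which form the glucose value is held, so confirm this before the wording is fixed. SAP 7.4 (below 3.0) and 11.7.3.1 (at or below 3.0) should also be reconciled.

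The cost is SAP wording, one more model run and less precision. With no true difference, 10 events per subject and k = 1, SE is √[(0.2 + 2)/275] = 0.089, and the 95% limits lie a factor of exp(1.96 × 0.089) = 1.19 either side of the estimate. With 0.5 events per subject and k = 3, SE is √[(4 + 6)/275] = 0.191 and the factor is 1.45. Rarer events would widen it further. The report should say that differences between arms in how often subjects self-test remain uncontrolled.
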